### 5.3 STUDY INTERVENTION/EXPERIMENTAL MANIPULATION ADHERENCE

We will track participants' attendance at intervention sessions and exposure to intervention materials by utilizing a PN encounter form. Here, patient navigators will record process data related to the PN services provided, including: 1) number of encounters, 2) length of time of each encounter; 3) barriers experienced by patients; and 4) actions taken to reduce barriers. This information will be recorded using the PN encounter form. Patient navigators will keep copies of the participants' safety plans and the SPI suicide risk curve. The patient navigators will also keep detailed qualitative notes regarding telephone, text, and in-person encounters with participants, including participants' progress in obtaining mental health services, successes in implementing the PN intervention, and challenges in implementing the PN intervention.

We will examine intervention adherence during the case series and open trial by calculating the number of PN encounters, number of intervention modules delivered, and how often each module is delivered. We will also review the progress notes to determine if participants carried out plans described in the progress notes (i.e., contact a mental health provider, enroll in a support group).

## 6 STUDY INTERVENTION/EXPERIMENTAL MANIPULATION DISCONTINUATION AND PARTICIPANT DISCONTINUATION/WITHDRAWAL

### 6.1 DISCONTINUATION OF STUDY INTERVENTION/EXPERIMENTAL MANIPULATION

If a subject chooses to discontinue from PN+SPI intervention but agrees to remain in the study, remaining study procedures (assessments) will be completed as indicated by the study protocol.

The data to be collected at the time of study intervention discontinuation will include the following:

- The reason(s) for discontinuing the participant from the intervention, and methods for determining the need to discontinue
- If the participant is due to complete assessments within 2 weeks of being discontinued from the study intervention, those assessments will be administered at the time of discontinuation; if the next scheduled assessments are more than 2 weeks from the discontinuation date, the discontinued participant will wait for the next scheduled assessment. Thereafter, the participant will be included in all future scheduled assessments, even though not participating in the intervention.

### 6.2 PARTICIPANT DISCONTINUATION/WITHDRAWAL FROM THE STUDY

In both the case series and open trial, participants are free to withdraw from participation in the study at any time upon request. An investigator may discontinue a participant from the study for the following reasons:

- The participant can no longer participate in the remainder of the study (e.g. long-term prison sentence, long-term hospitalization); or
- The participant loses their legal right to provide consent to participate for the remainder of the study.

The reason for participant discontinuation or withdrawal from the study will be recorded in an electronic system of tracking developed by the research team. Subjects who sign the informed consent form and receive the study intervention, and subsequently withdraw, or are discontinued from the study will not be replaced.

### 6.3 LOST TO FOLLOW-UP

For the case series, a participant will be considered lost to follow-up only if they fail to complete the three-month follow-up assessment within 31 days of when it was scheduled to be completed. For the open trial, a participant will be considered lost to follow-up only if they fail to complete the six-month follow-up assessment within 31 days of when it was scheduled to be completed. Otherwise, study staff will continue to attempt to contact the participant, unless the participant decides to withdraw from the study or 31 days has passed following the last scheduled follow-up.

The following actions will be taken to minimize loss to follow-up and missing data:

- At the baseline assessment, participants will complete a locator form, which asks permission for study staff to contact participants via phone, text, email, and mail. We also ask participants for their preferred contact method, and for the name and contact information of close friends/family member whom the study could contact in the event that staff are unable to connect with the participant. Study staff will utilize these multiple contact methods to schedule, or re-schedule, follow-up assessments as necessary.
- Study staff will contact participants on multiple days and times.
- Participants will be given multiple appointment reminders and study staff will confirm the scheduled appointment with the participant multiple times.
- Study staff will contact participants to schedule follow-up appointments within a month of each participant's next scheduled follow-up appointment (if they are unable to schedule the follow-up appointment at the time of the previous appointment).
- Upon rescheduling follow-up assessments, study staff will counsel the participant on the importance of maintaining the assigned visit schedule and ascertain if the participant wishes to continue in the study.
- The study team will meet weekly to discuss challenges faced in contacting participants and completing follow-up assessments and how to potentially overcome them.

#### 6.4 ENDPOINT AND OTHER NON-SAFETY ASSESSMENTS

##### **Case Series:**

Participants will complete the initial baseline assessment to confirm eligibility. Prior to beginning the baseline assessment procedures, a trained member of the study team will obtain informed consent. If the participant consents to participate in the study, the baseline assessment will be performed. Participants will complete self-report questionnaires (see below), clinician-based interviews (see below), and the first SPI+PN session (intake, introduction to navigation, and the SPI).

Post-baseline, participants will receive PN services for a period of three-months. Patient navigators will record PN intervention encounter data (see below). Participants will then complete a three-month follow-up assessment, consisting of clinician-based interviews (see below) and providing study and intervention feedback through open-ended survey questions (see below).

- Administration of self-report questionnaires:
  - Participants will complete self-report questionnaires in Qualtrics (either done remotely from their homes, or on a computer within the lab).
  - Self-report questionnaires include:
    - Demographics survey
      - Assesses demographic items (e.g. age, race, ethnicity, sex assigned at birth, gender identity, sexual orientation, relationship status, country of origin, U.S. citizen status, primary language, current grade in school or education level, health insurance status, employment status, income (if applicable))
      - Interpersonal Needs Questionnaire-15 (INQ-15)
        - Assesses thwarted belongingness and perceived burdensomeness

- INQ-15 has good structural validity, internal consistency, and concurrent validity
- Suicide-Related Coping Scale (SRCS)
  - Assesses external coping and internal coping
  - SRCS has good structural validity, internal consistency, sensitivity to change, and concurrent validity
- Acquired Capability for Suicide Scale – Fearlessness about Death (ACSS-FAD)
  - Assesses capability for suicide
  - ACSS-FAD has strong psychometric properties
- Minority Stressors self-report questionnaires
  - Heterosexist Harassment and Rejection Scale (HHRDS)
  - Internalized Homophobia Scale (IHP)
  - Sexual Orientation Concealment Scale (SOCS)
  - Gay-Related Rejection Sensitivity Scale (GRS)
  - Sexual Minority Women Rejection Sensitivity Scale (SMW-RSS)
  - Gender Minority Stress and Resilience Measure (GMSR)
    - Assess distal minority stress (e.g., victimization, rejection, and discrimination) and proximal minority stress (e.g., non-disclosure and internalized transphobia)
- Intersectional Discrimination Index (InDI)
  - Assesses intersectional discrimination
- Social support self-report questionnaires
  - Patient-Reported Outcome Measurement Information System (PROMIS) Emotional Support Scale – Short Form 8a
  - Patient-Reported Outcome Measurement Information System (PROMIS) Informational Support Scale – Short Form 8a
  - Patient-Reported Outcome Measurement Information System (PROMIS) Instrumental Support Scale – Short Form 8a
- Hurt, Insult, Threaten Screen (HITS)
  - Assesses intimate partner violence
- McLean Screening Instrument for Borderline Personality Disorder (MSI-BPD)
  - Assesses borderline personality disorder symptomology
- Client Satisfaction Questionnaire-8 (CSQ-8)
  - Assesses satisfaction with mental health care services received
  - CSQ-8 has high internal consistency
- Satisfaction with Interpersonal Relationship with PN
  - Assesses satisfaction with care provided by a patient navigator
  - Satisfaction with Interpersonal Relationship with PN has high internal consistency
- Dysmorphic Concern Questionnaire (DCQ)
  - Assesses dysmorphic symptoms
  - Adapted with modified instructions to better capture the Body Dysphoric Disorder phenotype and identify participants whose concerns were due to an objective disfigurement caused by a medical condition or injury
- Eating Disorder Examination-Questionnaire (EDE-Q)
  - Assesses eating disorder pathology

- Adapted with modified instructions to improve the measure's utility when evaluating objective binge eating in patients with Binge Eating Disorder
  - Adult ADHD Self-Report Screening Scale for DSM-5 (ASRS-5)
    - Assesses ADHD symptomatology
  - Satisfaction with Mental Health Care
    - Three open-ended questions created by investigative team
  - Open-ended survey questions
    - Used to obtain study and intervention feedback
- Clinician-administered interviews
  - Columbia-Suicide Severity Rating Scale (C-SSRS)
    - Assesses suicidal ideation, intent, plan, and behaviors
    - C-SSRS has strong psychometric properties (i.e. evidence of internal consistency, construct validity, predictive validity, incremental validity, and sensitivity to change)
  - Diagnostic Interview for Anxiety, Mood, Obsessive-Compulsive and Related Neuropsychiatric Disorders (DIAMOND)
    - Semi-structured diagnostic interview
    - Assesses psychiatric diagnoses among adults (aged 18+)
      - DIAMOND has very good inter-rater reliability, test-retest reliability, and convergent and divergent validity
    - Modules regarding the following disorders will be administered depending on responses to screening questions: Anxiety and Mood Disorders, Trauma and Stressor-Related Disorders, and Psychotic Disorders
  - Schedule for Affective Disorders and Schizophrenia for School-Age Children (K-SADS)
    - Computer-administered diagnostic interview
    - Assess psychiatric diagnoses among children (aged 15-17 in this study)
    - Modules regarding the following disorders will be administered depending on responses to screening questions: Anxiety and Mood Disorders, Trauma and Stressor-Related Disorders, and Psychotic Disorders
  - Cornell Services Index (Psychological Services section) - Adapted
    - Assesses the type(s) of psychological services obtained, the type of provider, the site of service, the reason for the visit, the frequency of service, and the number of minutes per visit during the past three months
    - Has good re-test and interrater reliability
    - Adapted by the study team to also collect data on:
      - Comorbid medical conditions
      - Medications prescribed
      - Date participant attended first mental health appointment following study enrollment
      - Number of mental health appointments attended following study enrollment
      - Types of mental health providers who treated the participant following study enrollment
  - Addiction Severity Index - Lite Version (ASI-Lite)
    - Assesses substance use
    - Interview questions to obtain feedback on the study and the intervention.
- Patient Navigator Data Collection
  - Patient navigators will audio-record PN sessions

- Patient navigators will record process data related to the PN provided, including:
  - Number of encounters
  - Length of time of each encounter
  - Barriers experienced by patients
  - Actions taken to reduce barriers
- Patient navigators will keep detailed qualitative notes regarding telephone, text, and in-person encounters with participants, including participants' progress in obtain mental health services, successes in implementing the PN intervention, and challenges in implementing the PN intervention
- Patient navigators will keep copies of the participants' safety plans and the SPI suicide risk curve

**Open Trial:**

Participants will complete the initial baseline assessment to confirm eligibility. Prior to beginning the baseline assessment procedures, a trained member of the study team will obtain informed consent. If the participant consents to participate in the study, the baseline assessment will be performed. Participants will complete self-report questionnaires (see below), clinician-based interviews (see below), and the first SPI+PN session (intake, introduction to navigation, and the SPI).

Post-baseline, participants will receive PN services for a period of six-months. Patient navigators will record PN intervention encounter data (see below). Participants will complete a three-month follow-up assessment, consisting of self-report questionnaires (see below) and clinician-based interviews (see below). Finally, participants will complete a six-month follow-up assessment, consisting of self-report questionnaires (see below), clinician-based interviews (see below), and a key informant interview.

- Administration of self-report questionnaires:
  - Participants will complete self-report questionnaires in Qualtrics (either done remotely from their homes, or on a computer within the lab).
  - Self-report questionnaires include:
    - Demographics survey
      - Assesses demographic items (e.g. age, race, ethnicity, sex assigned at birth, gender identity, sexual orientation, relationship status, country of origin, U.S. citizen status, primary language, current grade in school or education level, health insurance status, employment status, income (if applicable))
    - Interpersonal Needs Questionnaire-15 (INQ-15)
      - Assesses thwarted belongingness and perceived burdensomeness
        - INQ-15 has good structural validity, internal consistency, and concurrent validity
    - Suicide-Related Coping Scale (SRCS)
      - Assesses external coping and internal coping
        - SRCS has good structural validity, internal consistency, sensitivity to change, and concurrent validity
    - Acquired Capability for Suicide Scale – Fearlessness about Death (ACSS-FAD)

- Assesses capability for suicide
  - ACSS-FAD has strong psychometric properties
- Minority Stressors self-report questionnaires
  - Heterosexist Harassment and Rejection Scale (HHRDS)
  - Internalized Homophobia Scale (IHP)
  - Sexual Orientation Concealment Scale (SOCS)
  - Gay-Related Rejection Sensitivity Scale (GRS)
  - Sexual Minority Women Rejection Sensitivity Scale (SMW-RSS)
  - Gender Minority Stress and Resilience Measure (GMSR)
    - Assess distal minority stress (e.g., victimization, rejection, and discrimination) and proximal minority stress (e.g., non-disclosure and internalized transphobia)
- Intersectional Discrimination Index (InDI)
  - Assesses intersectional discrimination
- Social support self-report questionnaires
  - Patient-Reported Outcome Measurement Information System (PROMIS) Emotional Support Scale – Short Form 8a
  - Patient-Reported Outcome Measurement Information System (PROMIS) Informational Support Scale – Short Form 8a
  - Patient-Reported Outcome Measurement Information System (PROMIS) Instrumental Support Scale – Short Form 8a
- Hurt, Insult, Threaten Screen (HITS)
  - Assesses intimate partner violence
- McLean Screening Instrument for Borderline Personality Disorder (MSI-BPD)
  - Assesses borderline personality disorder symptomology
- Client Satisfaction Questionnaire-8 (CSQ-8)
  - Assesses satisfaction with mental health care services received
    - CSQ-8 has high internal consistency
  - Adapted by the study team to assess for satisfaction with patient navigation services received in addition to assessing for satisfaction with mental health care services received
- Satisfaction with Interpersonal Relationship with PN
  - Assesses satisfaction with care provided by a patient navigator
    - Satisfaction with Interpersonal Relationship with PN has high internal consistency
- Dysmorphic Concern Questionnaire (DCQ)
  - Assesses dysmorphic symptoms
  - Adapted with modified instructions to better capture the Body Dysphoric Disorder phenotype and identify participants whose concerns were due to an objective disfigurement caused by a medical condition or injury
- Eating Disorder Examination-Questionnaire (EDE-Q)
  - Assesses eating disorder pathology
  - Adapted with modified instructions to improve the measure's utility when evaluating objective binge eating in patients with Binge Eating Disorder
- Adult ADHD Self-Report Screening Scale for DSM-5 (ASRS-5)
  - Assesses ADHD symptomatology

- Difficulties in Emotion Regulation Scale-16
      - Assesses emotion regulation
    - Satisfaction with Mental Health Care
      - Three open-ended questions created by investigative team
- Clinician-administered interviews
  - Columbia-Suicide Severity Rating Scale (C-SSRS)
    - Assesses suicidal ideation, intent, plan, and behaviors
    - C-SSRS has strong psychometric properties (i.e. evidence of internal consistency, construct validity, predictive validity, incremental validity, and sensitivity to change)
  - Diagnostic Interview for Anxiety, Mood, Obsessive-Compulsive and Related Neuropsychiatric Disorders (DIAMOND)
    - Semi-structured diagnostic interview
    - Assesses psychiatric diagnoses among adults (aged 18+)
      - DIAMOND has very good inter-rater reliability, test-retest reliability, and convergent and divergent validity
    - Modules regarding the following disorders will be administered depending on responses to screening questions: Anxiety and Mood Disorders, Trauma and Stressor-Related Disorders, and Psychotic Disorders
  - Schedule for Affective Disorders and Schizophrenia for School-Age Children (K-SADS)
    - Computer-administered diagnostic interview
    - Assess psychiatric diagnoses among children (aged 15-17 in this study)
    - Modules regarding the following disorders will be administered depending on responses to screening questions: Anxiety and Mood Disorders, Trauma and Stressor-Related Disorders, and Psychotic Disorders
  - Cornell Services Index (Psychological Services section) - Adapted
    - Assesses the type(s) of psychological services obtained, the type of provider, the site of service, the reason for the visit, the frequency of service, and the number of minutes per visit during the past three months
    - Has good re-test and interrater reliability
    - Adapted by the study team to also collect data on:
      - Comorbid medical conditions
      - Medications prescribed
      - Date participant attended first mental health appointment following study enrollment
      - Number of mental health appointments attended following study enrollment
      - Types of mental health providers who treated the participant following study enrollment
  - Addiction Severity Index - Lite Version (ASI-Lite)
    - Assesses substance use
- Patient Navigator Data Collection
  - Patient navigators will audio-record PN sessions
  - Patient navigators will record process data related to the PN provided, including:
    - Number of encounters
    - Length of time of each encounter
    - Barriers experienced by patients
    - Actions taken to reduce barriers

- Patient navigators will keep detailed qualitative notes regarding telephone, text, and in-person encounters with participants, including participants' progress in obtain mental health services, successes in implementing the PN intervention, and challenges in implementing the PN intervention
- Patient navigators will keep copies of the participants' safety plans and the SPI suicide risk curve
- Key informant interview

## 6.5 SAFETY ASSESSMENTS

The Columbia-Suicide Severity Rating Scale (C-SSRS) will be used by the trained telephone screeners, assessors, and patient navigators to assess participant safety throughout both the case series and open trial. The Principal Investigators will train all personnel to use the C-SSRS and will be providing ongoing supervision. The C-SSRS is a clinician-based interview that assesses five types of suicidal ideation of increasing severity and four types of suicidal behavior, as well as the intensity of suicidal ideation. During the phone screen, items from the C-SSRS will be administered to determine participant eligibility, as well as assess participant safety. The C-SSRS will be administered during the baseline assessment to confirm participant eligibility, as well as assess participant safety. The C-SSRS will additionally be administered during each major assessment sessions and at the beginning of each intervention session.

Preliminary verification of eligibility will be completed (over the phone) in advance of the full baseline assessment visit. To manage suicide risk during the telephone screening or assessments (completed in person or remotely), the University of Washington Risk Assessment Protocol (UWRAP) will be used. Those who have enrolled in the study will receive additional support from their navigators following all assessments. A summary of how the UWRAP will be administered is as follows:

### Phone Screen:

1. Administer the introductory language and then administer and obtain verbal consent for telephone screening.
2. Administer the location/emergency contact items.
3. Administer the demographic inclusion criteria questions.
4. Administer items from the University of Washington Risk Assessment Protocol (UWRAP) regarding impairment as a result of substance use and the pre-assessment risk protocol (1: stress level; 2: urge to harm oneself; 3: intent to kill oneself; 4: urge to use substances) on a 1-7 point scale.
5. Administer items 1-3 from the UWRAP mood improvement protocol.
6. Administer phone screening items adapted from the Columbia-Suicide Severity Rating Scale.
7. Administer the UWRAP debrief checklist item 1 (obtain feedback on the telephone screening) plus items regarding re-assessment of risk (1: stress level; 2: urge to harm oneself; 3: intent to kill oneself; 4: urge to use substances) on a 1-7 point scale.
8. Administer the UWRAP debrief checklist items 5 and 6 (i.e., coping with negative feelings and suicidal ideation and description of fun activities planned for the day).
9. If potential participant has no suicidal intent and plan, engage in chit-chat and/or suggest

that they engage in the other activities in the UWRAP mood induction protocol item 4 before returning to their daily activities (for example, listen to music)

10. If a potential participant has suicidal intent and/or plan, administer the UWRAP debrief checklist items 8 and 9 (strategies to reduce suicide risk) and then UWRAP mood induction protocol item 4. The person conducting the phone screening should stay on the telephone with the potential participant while they do their activity or chat). After the potential participant has completed their mood induction activity, the phone screener should administer item 5 on UWRAP mood induction protocol (i.e., rating the effect of the activity on their mood).
11. Consult with the clinician “on call” for those with suicidal intent and plan who are unable to guarantee that they will use behavior strategies (for example, to keep themselves safe for 24 hours) who may then contact emergency services.
12. The Principal Investigators should be contacted when any participant expresses suicidal intent and/or plan, based on their responses to the Columbia-Suicide Severity Rating Scale.

Baseline Assessment:

1. Administer the introductory language and then engage in the informed consent procedures for the study.
2. Administer the location/emergency contact items.
3. Administer three items from the University of Washington Risk Assessment Protocol (UWRAP) regarding impairment as a result of substance use and the pre-assessment risk protocol (1: stress level; 2: urge to harm oneself; 3: intent to kill oneself; 4: urge to use substances) on a 1-7 point scale.
4. Administer items 1-3 from the UWRAP mood improvement protocol.
5. Complete the baseline assessment.
6. Administer the UWRAP debrief checklist item 1 (obtain feedback on the telephone screening) plus items regarding re-assessment of risk (1: stress level; 2: urge to harm oneself; 3: intent to kill oneself; 4: urge to use substances) on a 1-7 point scale.
7. Administer the UWRAP debrief checklist items 5 and 6 (i.e., coping with negative feelings and suicidal ideation and description of fun activities planned for the day).
8. If participant has no suicidal intent and plan, engage in chit-chat and/or suggest that they engage in the other activities in the UWRAP mood induction protocol item 4 before returning to their daily activities (for example, listen to music)
9. If the participant remains distressed, administer the UWRAP mood induction protocol item 4. Stay on the videoconference/or with the potential participant while they do their activity or chat. After the participant has completed their mood induction activity, administer item 5 on UWRAP mood induction protocol (i.e., rating the effect of the activity on their mood).
10. Consult with the clinician “on call” for those with suicidal intent and plan who are unable to guarantee that they will use behavior strategies (for example, to keep themselves safe for 24 hours) who may then contact emergency services.
11. The Principal Investigators should be contacted when any participant expresses suicidal intent and/or plan, based on their responses to the Columbia-Suicide Severity Rating Scale.
12. Transfer participant to the patient navigator. The patient navigator will implement the intake session of the patient navigation intervention, which includes the Safety Planning Intervention.

Follow-up Assessment:

1. Administer the introductory language and the location/emergency contact items.
2. Administer three items from the University of Washington Risk Assessment Protocol (UWRAP) regarding impairment as a result of substance use and the pre-assessment risk protocol (1: stress level; 2: urge to harm oneself; 3: intent to kill oneself; 4: urge to use substances) on a 1-7 point scale.
3. Administer items 1-3 from the UWRAP mood improvement protocol.
4. Complete the follow-up assessment.
5. Assessor administer the UWRAP debrief checklist item 1 (obtain feedback on the telephone screening) plus items regarding re-assessment of risk (1: stress level; 2: urge to harm oneself; 3: intent to kill oneself; 4: urge to use substances) on a 1-7 point scale.
6. Assessor administer the UWRAP debrief checklist items 5 and 6 (i.e., coping with negative feelings and suicidal ideation and description of fun activities planned for the day).
7. If participant has no suicidal intent and plan, the assessor should engage in chit-chat and/or suggest that they engage in the other activities in the UWRAP mood induction protocol item 4 before returning to their daily activities (for example, listen to music)
8. If the participant remains distressed, the assessor should administer the UWRAP mood induction protocol item 4. The assessor should stay on the videoconference/or with the potential participant while they do their activity or chat. After the participant has completed their mood induction activity, the assessor should administer item 5 on UWRAP mood induction protocol (i.e., rating the effect of the activity on their mood).
9. Consult with the clinician “on call” for those with suicidal intent and plan who are unable to guarantee that they will use behavior strategies (for example, to keep themselves safe for 24 hours) who may then contact emergency services.
10. The Principal Investigators should be contacted when any participant expresses suicidal intent and/or plan, based on their responses to the Columbia-Suicide Severity Rating Scale.
11. Transfer participant with suicidal intent and plan to the patient navigator. The patient navigator will go over the safety plan with the participant and will administer PN module 6: Suicidal Crisis Management.

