### 6.6.3 CLASSIFICATION OF AN ADVERSE EVENT

#### 6.6.3.1 SEVERITY OF EVENT

The Principal Investigators, in consultation with physician Co-Investigator [name] and other Co-Investigator [name], if necessary, will assess the severity of adverse events as either: 1) Grade 1: Mild; 2) Grade 2: Moderate; 3) Grade 3: Severe; 4) Grade 4: Life threatening; or 5) Grade 5: Death. The following definitions will be used to assign a severity rating:

1. **Grade 1 Mild:** asymptomatic or mild symptoms; clinical or diagnostic observations only; no intervention indicated.
2. **Grade 2 Moderate:** minimal, local or noninvasive intervention indicated; limiting age-appropriate instrumental activity of daily living.
3. **Grade 3 Severe or medically significant but not immediately life-threatening:** hospitalization or prolongation of hospitalization indicated; disabling; limiting self-care activities of daily living.
4. **Grade 4 Life-threatening consequences:** urgent intervention indicated.
5. **Grade 5 Death related to adverse event.**

Because the study focuses on suicide prevention, adverse events related to suicidal ideation, suicidal behaviors, and other types of self-harm will be graded for severity using the following guidelines:

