#### **Grade 2:**

1. Development of new suicide intention or plan
2. Engaging in self-harm behaviors which do not require hospitalization
3. Engaging in self-harm behaviors which require an ER visit but not inpatient hospitalization

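### At follow-up, the navigator transfer and the on-call consult require both suicidal intent and a plan, so intent without a plan triggers only Principal Investigator contact as an intent-specific step

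*Combined protocol and SAP*

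**What the plan says.** Section 6.5, Follow-up Assessment, sets three escalation steps:

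- Step 9: the on-call clinician is consulted "for those with suicidal intent and plan who are unable to guarantee that they will use behavior strategies". That clinician may then call emergency services.
- Step 10: "The Principal Investigators should be contacted when any participant expresses suicidal intent and/or plan", judged from the C-SSRS responses.
- Step 11: "Transfer participant with suicidal intent and plan to the patient navigator". The navigator then reviews the safety plan and delivers Module 6, Suicidal Crisis Management.

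Steps 1 to 6 (risk ratings, the assessment itself, debrief) apply to everyone. Step 8, the mood-induction activity, depends on remaining distress. Step 7 is the low-risk route: "If participant has no suicidal intent and plan, the assessor should engage in chit-chat".

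The other two lists in 6.5 differ. Phone-screen step 10 says: "If a potential participant has suicidal intent and/or plan, administer the UWRAP debrief checklist items 8 and 9 (strategies to reduce suicide risk"), and the screener stays on the line during the mood activity. Baseline step 12 hands every participant to the navigator, whatever they reported.

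Before the lists, 6.5 adds a general promise: "Those who have enrolled in the study will receive additional support from their navigators following all assessments".

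**The concern.** Steps 9 and 11 join intent and plan with *and*, while step 10, between them, uses *and/or*. An assessor who follows the list will treat them as different rules. Section 6.4 describes the C-SSRS as covering intent and plan as distinct items, so intent without a plan can be recorded at a visit.

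The population makes this a practical matter. Everyone enrolled has a past suicide attempt and recent ideation (4.1), and some are minors who consent for themselves (2.3.3). A participant who states intent and cannot promise to stay safe, but names no plan, does not meet the written trigger for the on-call clinician. Nor do they meet the trigger for the handover that brings safety-plan review and Module 6, which includes emergency services and help in reaching a higher level of care (3.1, Table 1).

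**Working it through.** No sample size, power or error rate is involved. The check applies the written triggers to each possible case and compares the three lists.

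**1. Follow-up triggers, case by case.** Two inputs define the cases: what is stated (intent only, plan only, both) and whether the participant can guarantee safety. That gives 3 × 2 = 6 combinations.

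| Stated | Guarantees safety | Step 9: on-call clinician | Step 10: Principal Investigators | Step 11: navigator transfer |
|---|---|---|---|---|
| Intent only | yes | no | yes | no |
| Intent only | no | no | yes | no |
| Plan only | yes | no | yes | no |
| Plan only | no | no | yes | no |
| Both | yes | no | yes | yes |
| Both | no | yes | yes | yes |
| **Triggered** | | **1 of 6** | **6 of 6** | **2 of 6** |

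With *and/or* in steps 9 and 11, and the guarantee condition kept in step 9, step 9 covers the three rows without a guarantee (3 of 6) and step 11 covers all rows (6 of 6). Step 10 stays at 6 of 6. For intent only without a guarantee, the steps triggered rise from 1 of 3 to 3 of 3. The counts describe the rule; they do not say how often each case occurs.

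**2. The three lists side by side.**

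| Response | Phone screen | Baseline | Follow-up |
|---|---|---|---|
| Principal Investigator contact | either (step 12) | either (step 11) | either (step 10) |
| On-call clinician | both, no guarantee (step 11) | both, no guarantee (step 10) | both, no guarantee (step 9) |
| Debrief items 8 and 9 | either (step 10) | not listed | not listed |
| Navigator transfer | not yet enrolled | everyone (step 12) | both (step 11) |

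The on-call trigger is the same throughout. What narrows at follow-up is the navigator transfer, from everyone at baseline to intent and plan. The phone screen's response to either one alone also has no follow-up counterpart. At baseline, the gap is confined to the on-call step.

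**3. Where it matters most.** Navigation lasts six months in the open trial and three months in the case series, and the last follow-up falls at the same point (6.4). The planned final visits number up to 30 + 10 = 40. No later session is scheduled at which the C-SSRS would be repeated. At the open-trial three-month visit navigation continues, with contact at least monthly (5.1.1), and each session opens with the C-SSRS (6.6.4). Intent would be asked about again.

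**The case against.** The strongest defence is that this is a deliberate tiered design: the Principal Investigators for either sign, the on-call clinician only for both plus no safety guarantee. The on-call trigger is identical in all three lists, and the exclusion criterion in 4.2 also joins intention and plan. Step 10 matters too. The Principal Investigators train and supervise C-SSRS users (6.5), judge risk at entry (4.2) and decide on clinical worsening (6.6.4), and nothing stops them from calling in the clinician or the navigator. Navigator support is promised after all assessments, which includes the last one, and modules are delivered according to need (3.1, 5.1.1). Finally, 6.5 calls its lists a summary, and the Manual of Procedures and SOPs named in 8.1.7 are not among the documents.

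Much of this stands, and it limits the point. The on-call threshold may well be intended, so the transfer in step 11 is the firmer half. Every intent-only participant does reach the Principal Investigators, but no action after that contact is written. If the general navigator support already meant safety-plan review and Module 6 for everyone, step 11 would be redundant. The criterion in 4.2 governs eligibility, not response, and the phone screen that applies it still responds to either sign. The fuller manuals may hold a broader rule, but a summary should not state a narrower trigger than the one meant.

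Two stronger readings are tempting:

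- A reader might infer that step 7 sends intent-only participants to small talk and then home. Phone-screen steps 9 and 10 argue against this: the same phrase, followed by a step for either sign, makes sense only if it means neither. Step 7 is loosely worded and merits clarification only.
- A reader might infer that the adverse-event grading makes intent alone a call for intervention, since 6.6.3.1 places "Development of new suicide intention or plan" in Grade 2 and its general Grade 2 text says "minimal, local or noninvasive intervention indicated". But suicide-related events have their own grading guidelines. Grades label severity and do not trigger responses, and Principal Investigator contact with navigator support could meet the general wording.

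**Conclusion.** The point holds as a narrow inconsistency in a stated safety rule. At follow-up, intent without a plan triggers Principal Investigator contact as the one intent-specific step, plus general navigator support of unstated content and timing. It does not trigger the on-call consult or the transfer for safety-plan review and Module 6, even when safety cannot be guaranteed. That is less than phone-screen step 10 and baseline step 12 provide, and it weighs most at final visits. The conclusion rests on reading steps 9 to 11 as written; an unseen manual could broaden them.

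The number of participants concerned is unknown, because the documents give no rate of intent without a plan. A reader might take all planned follow-ups (30 × 2 + 10 = 70) as affected, but that is simply the total number of visits.

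A reader might also infer that intent-only participants are left without a navigator, or that no outside contact would be made for a minor in crisis. Neither follows. Section 6.5 promises navigator support to all enrolled participants. Section 2.3.3 already commits staff to contacting a trusted adult in a psychiatric emergency, and both the baseline and follow-up lists include emergency-contact items.

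**What to change.** In section 6.5:

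1. Follow-up step 11: replace intent *and* plan with intent *and/or* plan.
2. Follow-up step 9: make the same replacement and keep the condition that the participant cannot guarantee safety. For consistency, change the matching on-call steps, baseline step 10 and phone-screen step 11.
3. As a clarification only, write *neither suicidal intent nor plan* in follow-up step 7 and baseline step 8.

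This is a wording change in six steps (four triggers, two clarifications) and uses the existing navigators and on-call clinician. The cost is some additional navigator handovers, for plan-only as well as intent-only participants, and a few more on-call consults, since step 9 still requires inability to guarantee safety. The number of either cannot be estimated from the documents.
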